4.1.2 Treatment Groups

Statistics will be displayed for the following treatment groups:

- Colistimethate Sodium
- Placebo
- Overall

4.1.3 Descriptive Statistics

Descriptive statistics will be used to summarise all efficacy and safety results.

Descriptive statistics for quantitative variables will include n (the number of observations, i.e. non-missing values), mean, standard deviation (SD), median, minimum and maximum values. The 25th and 75th percentiles will also be presented where clearly stated.

Categorical variables will be summarised by using frequency count and percent distributions. Percentages will be calculated using the total number of subjects per treatment/population.

4.1.4 Statistical Significance

The analysis of the trial is on a comparative basis. For all efficacy parameters, comparisons will be made between colistimethate sodium and placebo. Two-sided p-values <0.05 will be considered statistically significant and 95% two-sided confidence intervals (CIs) will be presented where appropriate. No adjustment for multiplicity testing will be adopted. A hierarchical testing procedure will be applied to the secondary endpoints as detailed in Section 4.7.5.

4.1.5 Subgroup Analyses

The mean annual NCFB pulmonary exacerbation rate will also be estimated classifying subjects by:

- Number of NCFB pulmonary exacerbations requiring oral or intravenous antibiotics in the 12 months prior to study entry.

The number of NCFB pulmonary exacerbations requiring oral antibiotics in the last 12 months and the number of NCFB pulmonary exacerbations requiring intravenous antibiotics in the last 12 months prior to study entry, as collected in the eCRF Screening folder on the Non-CF Bronchiectasis History form, will be summed.

CONFIDENTIAL

Sponsor:	Zambon S.p.A.	Protocol Number:	Z7224L01
----------	---------------	------------------	----------

Results will be presented for subjects with 1, 2 and >2 NCFB pulmonary exacerbations in the last 12 months.

If a subject has no data regarding the number of NCFB pulmonary exacerbations requiring oral and/or intravenous antibiotics in the last 12 months prior to study entry the subject will be excluded from the analysis.

- Previous usage of colistimethate sodium/colistin (as collected on the Non-CF Bronchiectasis History eCRF form).

Based on data collected on the Non-CF Bronchiectasis History eCRF form regarding previous usage of Colistimethate Sodium/colistin, the subjects will be classified into:

- Without any previous usage of colistimethate sodium/colistin;
- With previous usage of colistimethate sodium/colistin.

Subjects with missing data regarding previous usage of colistimethate sodium/colistin will be excluded from the analysis.

CC1 will be presented classifying subjects by status of previous usage of colistimethate sodium/colistin as collected on the Non-CF Bronchiectasis History eCRF form. Subjects with missing data regarding previous usage of colistimethate sodium/colistin will be included in the analysis in a separate subgroup.

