7.2. SELECTION OF SUBJECTS

7.2.1. INCLUSION CRITERIA

Subjects can be included in the trial if they meet all the inclusion criteria listed below:

- 1) are able and willing to give informed consent, following a detailed explanation of participation in the protocol and signed consent obtained;
- 2) are aged 18 years or older of either gender;
- 3) are diagnosed with NCFB by computerised tomography (CT) or high resolution CT (HRCT) as recorded in the subject's notes and this is their predominant condition being treated;
- 4) had at least 2 NCFB pulmonary exacerbations requiring oral or inhaled antibiotics or 1 NCFB pulmonary exacerbation requiring intravenous antibiotics in the 12 months preceding the Screening Visit (Visit 1) and had no NCFB pulmonary exacerbation with or without treatment during the period between Visit 1 and Visit 2;
- 5) have a documented history of *P. aeruginosa* infection;
- 6) are clinically stable and have not required a change in pulmonary treatment for at least 30 days before the Screening Visit (Visit 1);
- 7) have pre-bronchodilator FEV₁ \geq 25% of predicted;
- 8) had a positive sputum culture for *P. aeruginosa* from an adequate sample taken at the Screening Visit (Visit 1) or during the screening period.

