Section 2: Summary; Population	Inclusion criteria #3 has been amended from “diagnosed with NCFB by computerised tomography (CT) or high-resolution CT (HRCT) as recorded in the subject’s notes” to “are diagnosed with NCFB by computerised tomography (CT) or high-resolution CT (HRCT) as recorded in the subject’s notes and this is their predominant condition being treated”.	Amended to emphasize and clarify that NCFB should be the predominant condition experienced by the study patient requiring treatment (as opposed to, for example, chronic obstructive pulmonary disease.
	Inclusion criteria #4 amended to allow patients experiencing 2 NCFB pulmonary exacerbations requiring inhaled antibiotics to be enrolled.	Discussions with sites have indicated that inhaled antibiotics are routinely being used at several sites and not just oral antibiotics as routine management for patients with NCFB pulmonary exacerbations.
	Inclusion criteria #7 has been amended to allow patients with a pre-bronchodilator FEV ₁ ≥25% (as opposed to ≥30%).	The FEV ₁ level has been adjusted downwards after consultation with experts in the field who agree this cut off level

		would not negatively impact the study in terms of safety but would help with recruitment.
	Inclusion criteria #8 has been amended to reflect the fact that any positive result for one of the three potential sputum samples collected during the periods between Visit 1 and Visit 2 allows for patient inclusion.	Amended to reflect the sputum sample collection details documented in relevant sections of the study protocol.
	Exclusion criteria #3 has been amended to remove the reference to myeloproliferative disease.	This was an exclusion criterion in the Zambon phase 2 trial but has not been an exclusion criteria in similar phase 3 trials. Removal of this exclusion criteria will have no negative impact on the safety of the trial or efficacy assessments. There are no known confounding factors with NCFB and myeloproliferative disease. Other exclusion criteria will ensure patient safety; in particular exclusion criteria #20 (as renumbered).
	Exclusion criteria #8 has been deleted in its entirety.	The amendment to inclusion criteria #3 detailed above makes this exclusion criterion redundant.

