This document presents the Statistical Analysis Plan (SAP) for Zambon, Protocol No. Z7224L01: A double-blind, placebo-controlled, multi-centre, clinical trial to investigate the efficacy and safety of 12 months of therapy with inhaled colistimethate sodium in the treatment of subjects with non-cystic fibrosis bronchiectasis chronically infected with *Pseudomonas aeruginosa* (*P. aeruginosa*)

This analysis plan is based on the final protocol Version 7.0 dated 22Oct2019.

The SAP provides the description of the analysis for the final analyses. Any deviations from the SAP which occur after breaking the blind will be documented and justified in the final clinical trial report (CTR) and deviations will be clearly marked as 'post hoc' analysis.

CONFIDENTIAL

Sponsor:	Zambon S.p.A.	Protocol Number:	Z7224L01
----------	---------------	------------------	----------

2 Study Objectives

The primary objective of the trial is to investigate the effect of the use of inhaled colistimethate sodium, administered twice daily via the **CCI** for 12 months, compared to placebo in subjects with non-cystic fibrosis bronchiectasis (NCFB) chronically infected with *P. aeruginosa* on the annualized frequency of pulmonary exacerbations.

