4.4.3 Non-CF Bronchiectasis History

The following variables will be summarised for the mITT Population by treatment group and overall:

- Time since diagnosis of non-CF bronchiectasis (years);
- Diagnostic technique used (computerised tomography [CT] or high resolution CT: Yes or No);
- Number of lobes affected (1, 2, 3, more than 3);
- Underlying cause of the bronchiectasis;
- Number of NCFB pulmonary exacerbations requiring oral antibiotics in the last 12 months before Screening;
- Number of NCFB pulmonary exacerbations requiring intravenous antibiotics in the last 12 months before Screening;
- Previous usage of colistimethate sodium/colistin;
- Having at least 1 positive sputum culture for *P. aeruginosa* before Screening.

Notes:

- Time since diagnosis of NCFB (years) will be calculated as (date of Visit 1 – date of diagnosis of NCFB)/365.25;
- In order to calculate the time since diagnosis of NCFB, the following rules will be applied for partial dates of the date of diagnosis of NCFB:
 - if only the day is missing, the first day of the month will be assumed;
 - if the day and the month are missing, then the first day of the year will be assumed.

CONFIDENTIAL

Sponsor:	Zambon S.p.A.	Protocol Number:	Z7224L01
----------	---------------	------------------	----------

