4.7.4.3 CCI Analysis on Adherent Subjects

The primary analysis will also be repeated considering the subgroup of mITT subjects who were considered adherent, i.e. had an adherence of at least 80%.

4.7.4.4 Further Investigation: Number of Pulmonary Exacerbations in the 12 Months Prior to Study Entry

To further investigate any possible factor that might affect the mean annual NCFB pulmonary exacerbation rate, an exploratory negative binomial model will be fitted for the mITT population considering as an extra covariate the number of NCFB pulmonary exacerbations requiring oral or intravenous antibiotics in the 12 months prior to study entry.

4.7.4.5 Further Investigation: Stratified Analysis by Number of Pulmonary Exacerbation Requiring Oral or Intravenous Antibiotics in the 12 Months Prior to Study Entry

The number of NCFB pulmonary exacerbations requiring oral antibiotics in the last 12 months and the number of NCFB pulmonary exacerbations requiring intravenous antibiotics in the last 12 months prior to study entry, as collected in the eCRF Screening folder on the Non-CF Bronchiectasis History form, will be summed.

Analysis will be performed with the same criteria and methods as described for the primary efficacy model. If a subject has no data regarding the number of NCFB pulmonary exacerbations requiring oral and/or intravenous antibiotics in the last 12 months prior to study entry the subject will be excluded from the analysis.

A stratified analysis will also be performed classifying subjects according to the number of pulmonary exacerbations requiring oral or intravenous antibiotics in the 12 months prior to study entry, as reported in [Section 4.1.5](#).

4.7.4.6 Further Investigation: Stratified Analysis by Previous Usage of Colistimethate Sodium/Colistin

A stratified analysis will also be performed by previous usage of colistimethate sodium/colistin (as collected on the Non-CF Bronchiectasis History eCRF form) as reported in [Section 4.1.5](#).

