The number of subjects considered in the model in each treatment group will be presented. The value of δ at which the conclusion changes from favourable to unfavourable (i.e. where the p-value increases to above 0.05; that is, where the imputed number of pulmonary exacerbations in the Colistimethate Sodium group has to increase by 100 δ % for statistical significance to be lost) will be presented, along with the smallest value of δ for which the p-value remains below 0.05.

For each of these 2 values of δ , the adjusted mean NCFB pulmonary exacerbation rates and 95% CIs in each treatment group, the adjusted rate ratio and 95% CI, and the p-value from the multiple imputation analysis using that value of δ will also be presented.

6.1.2. **CCI** Analyses with Additional Covariates and Interactions

In order to explore the statistical evidence for the degree of consistency of treatment effect at each level of a given prognostic factor, the negative binomial model used for the primary analysis will be repeated with the following additional effects included (one model per bullet point below):

- Country-by-treatment interaction;
- Number of NCFB pulmonary exacerbations requiring oral or intravenous antibiotics in the 12 months prior to study entry (# exacerbations) (1; 2; >2) and # exacerbations-by-treatment interaction;
- Previous usage of colistimethate sodium/colistin (Yes; No) and previous usage-by-treatment interaction;

This document is confidential.

- Age (as a continuous covariate) and age-by-treatment interaction;
- Age group (<65 years; >=65 years) and age group-by-treatment interaction;
- Gender (Female; Male) and gender-by-treatment interaction.

As was done for the primary analysis, the adjusted mean annual NCFB pulmonary exacerbation rates in each treatment group and the adjusted rate ratio with their 95% CIs will be estimated by the model. The number of subjects considered in the model will be provided by treatment group. P-values of the effects and interactions based on Wald chi-square test will also be presented.

6.1.3. [REDACTED] Analyses by Subgroup

The primary model was already fitted separately for each country, for each # exacerbations (1; 2; >2), and for each previous usage of colistimethate sodium/colistin (Yes; No) category, as planned in Sections 4.7.4, 4.7.4.5 and 4.7.4.6, respectively, of the Final SAP v2.0 dated 8th April 2021.

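### SAP 4.1.5 counts only oral and intravenous prior exacerbations, so a patient admitted on inhaled-treated episodes scores 0 (no class) or 1

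*SAP*

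**What the plan says.** Protocol 7.2.1, criterion 4, requires that the patient "had at least 2 NCFB pulmonary exacerbations requiring oral or inhaled antibiotics or 1 NCFB pulmonary exacerbation requiring intravenous antibiotics" in the year before Screening. The inhaled route was a deliberate addition. The summary of changes attached to protocol v7.0 records: "Inclusion criteria #4 amended to allow patients experiencing 2 NCFB pulmonary exacerbations requiring inhaled antibiotics to be enrolled". The reason given there is that several sites routinely manage exacerbations with inhaled antibiotics.

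The SAP ties itself to that protocol version: "This analysis plan is based on the final protocol Version 7.0 dated 22Oct2019". Its Section 4.1.5 nevertheless defines the subgroup factor as "Number of NCFB pulmonary exacerbations requiring oral or intravenous antibiotics in the 12 months prior to study entry". The factor is the sum of two fields on the Non-CF Bronchiectasis History form, one oral and one intravenous. The SAP then says: "Results will be presented for subjects with 1, 2 and >2 NCFB pulmonary exacerbations in the last 12 months". Subjects with no data on these fields are excluded. No rule is given for a recorded count of zero.

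The same count appears elsewhere:
- The baseline history in SAP 4.4.3 lists "Number of NCFB pulmonary exacerbations requiring oral antibiotics in the last 12 months before Screening" and the intravenous equivalent, but no inhaled count.
- SAP 4.7.4.4 fits a model "considering as an extra covariate the number of NCFB pulmonary exacerbations requiring oral or intravenous antibiotics in the 12 months prior to study entry".
- SAP 4.7.4.5 stratifies by the 4.1.5 classes.
- Addendum 6.1.2 adds the count, at levels 1, 2 and >2, with its interaction with treatment.
- Addendum 6.1.3 plots the rate ratios by those levels.

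The statistical part of the protocol summary (Section 2) names prior-year exacerbation frequency as a covariate without restricting it by antibiotic route. SAP 4.13, which lists changes from the protocol, does not mention the restriction.

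**The concern.** Eligibility and analysis use different definitions of a prior exacerbation. The entry rule counts inhaled-treated episodes and the analysis variable does not, so a correctly enrolled patient can have an analysis value below what the entry rule requires. Some of these values fall outside every class the SAP provides.

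The affected analyses are meant to show whether the treatment effect is the same across levels of prior exacerbation burden. The Addendum gives internal consistency as one of its purposes and links it to a submission resting on a single pivotal trial. A consistency analysis that omits or misplaces eligible mITT subjects by rule, without saying so, is weaker than it looks. A small class can also be shifted by a few misplaced subjects.

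**Working it through.** No sample-size or power figure of the plan bears on this point. The check applies the two written rules to the same histories.

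**Inputs.** Let o, i and v be the prior-year numbers of exacerbations treated orally, by inhalation and intravenously, each episode counted under one route.
- Eligible under criterion 4 (protocol 7.2.1): o + i ≥ 2, or v ≥ 1.
- Eligible without the inhaled route: o ≥ 2, or v ≥ 1.
- SAP score (4.1.5): S = o + v, with classes 1, 2 and >2.
- Count matching criterion 4: T = o + i + v.

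**Step 1: patients who need the inhaled route.** They satisfy the first condition but not the second, so o ≤ 1, v = 0 and i ≥ 2 − o. Hence S = o + 0, which can only be 0 or 1, while T = o + i ≥ 2.

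**Step 2: enumeration.** With o from 0 to 3, i from 0 to 3 and v from 0 to 2, five histories depend on the inhaled route:

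| o, i, v | SAP score S | SAP class | Criterion-4 count T | Class on T |
|---|---|---|---|---|
| 0, 2, 0 | 0 | none | 2 | 2 |
| 0, 3, 0 | 0 | none | 3 | >2 |
| 1, 1, 0 | 1 | 1 | 2 | 2 |
| 1, 2, 0 | 1 | 1 | 3 | >2 |
| 1, 3, 0 | 1 | 1 | 4 | >2 |

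A score of 0 fits no class in 4.1.5 or 4.7.4.5 and no level in Addendum 6.1.2. If the form were left blank instead of zero, the missing-data rule would exclude the patient, so either way the patient leaves the class-based analyses. In 4.7.4.4 the coding of the covariate is not stated. If it is linear, 0 enters as a value and nobody is dropped. The 4.4.3 table drops nobody.

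**Step 3: other eligible patients.** None of them scores 0; the minimum is 1. On the same grid 12 of their histories still change class when inhaled episodes are counted. For example, (2, 1, 0) goes from 2 to >2, and (0, 1, 1) from 1 to 2.

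**Step 4: after counting all three routes.** No eligible patient scores 0, and the only eligible history in class 1 is (0, 0, 1), a single intravenous episode.

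**Step 5: how many subjects.** The documents do not say. Patients in Step 1 could enter only under v7.0, dated 22 October 2019. SAP 3.9 gives 342 randomised subjects in the blinded data of 15 January 2020 and 377 in total: 377 − 342 = 35, and 35 / 377 = 9.3%. Entries under v7.0 before that date are unknown. So is the share of v7.0 entrants who needed the inhaled route.

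**The case against.** The best defence is that the endpoint itself requires systemic antibiotics, which protocol 8.7 and 10.1 describe as oral or intravenous. A prior count of oral and intravenous episodes is then the like-for-like predictor, and adding inhaled-only episodes is not obviously better. That is a legitimate choice. But the SAP does not give this reason, and it would still leave a score of 0 without a class.

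The history form is not in the documents. Sites may have entered inhaled-treated episodes in the oral field, or recorded an episode treated by both routes as oral. This stands: the mismatch is certain on the written rules, but actual misclassification is not shown.

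The Addendum was written after the class analysis had been run. Its Section 6.1.3 names three countries whose rate ratios could not be calculated, yet it repeats the levels 1, 2 and >2 and says nothing of zero counts. This is weak evidence that nobody was lost, not proof.

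Finally, 4.7.4.4 is labelled exploratory, 4.7.4.5 is a further investigation, and the Addendum is post hoc and itself says that the trial is not powered for subgroups. This limits the weight of the point but does not remove it, because the rule as written gives a wrong result and is cheap to correct.

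**Conclusion.** The point holds as a mismatch between two written rules. Any patient who needs inhaled-treated episodes to qualify scores 0 or 1 in the SAP against a criterion-4 count of at least 2, and a 0 has no place in the class-based analyses. This follows by logic and assumes only that sites completed the oral and intravenous fields as labelled. The number of such patients is unknown and could be zero. The consequence is confined to exploratory and post hoc consistency analyses.

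A reader might infer more, without support in the documents:
- **That the primary result is at risk.** The primary negative binomial model (SAP 4.7.4) does not use this count.
- **That a head count follows from applying a percentage to all 377.** The route that produces a score of 0 opened only with v7.0, so 377 is the wrong base, and no share is given.
- **That these patients would be flagged as entry violators and removed from the PP population.** SAP 4.3 takes eligibility deviations from the eCRF. SAP 4.10.1 leaves exclusions to a joint CRO and sponsor decision before unblinding. The statistician's check in 4.10.2 is made only where feasible. Nothing makes the oral plus intravenous sum the eligibility test.
- **That milder patients are placed among the most severe.** The classes are event counts and class 1 is the lowest. Severity is defined separately in SAP 4.7.4, by intravenous antibiotics or hospitalisation.

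**What to change.** Where inhaled-treated counts were collected or can be queried, define the prior-12-month count to match criterion 4 (oral + inhaled + intravenous). List the inhaled count in SAP 4.4.3, and use the total in 4.1.5, 4.7.4.4, 4.7.4.5 and Addendum 6.1.2 and 6.1.3. Protocol 9.1.1 collects details of prior-year exacerbations, but it does not show that a route-specific inhaled count exists, so this needs checking first.

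Otherwise keep the oral and intravenous count, and:
- make the lowest class hold 0 (for example 0–1, or a separate 0 class), so that no mITT subject is dropped;
- state how 0 enters each model;
- declare the oral and intravenous restriction in SAP 4.13, with its reason.

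The cost is one derived variable, a few lines of text and possibly a limited site query for subjects whose oral plus intravenous sum is below the entry requirement. The Addendum states that the database is locked and the trial unblinded, so any re-run would be documented and marked as post hoc under the SAP's own rule in Section 1. Reporting how many mITT subjects score 0, and how many score 1 without an intravenous episode, would show at once whether the issue has any practical effect.

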4.1.6 Definition of Baseline

Age, height, weight and Body Mass Index (BMI) recorded at Visit 1 will be presented as baseline characteristics.

For 12-lead ECG, vital signs, physical examination and haematology, clinical chemistry and renal function parameters, baseline values are those recorded at Screening (Visit 1). If no assessment has been conducted at that visit, the last available value before IMP first dose (collected during unscheduled visits before IMP first dose) will be considered as baseline.

For sputum analysis, CC1 and spirometry baseline values are those recorded at Visit 2 before IMP first dose. If no assessment has been conducted at that visit, the last available value before IMP first dose (collected at the Screening visit or unscheduled visits before IMP first dose) will be considered as baseline.

4.1.7 Definition of Follow-up Time

All the efficacy analyses are focused on the endpoints collected during the treatment period. For these analyses, the follow-up time will not include the time from end of treatment to the follow-up call.

The follow-up time in days will be calculated using the following formula:

- Follow-up time (days) = [date of treatment completion/discontinuation - date of first IMP dose + 1].

The follow-up time in years will be calculated using the following formula:

CONFIDENTIAL

Sponsor:	Zambon S.p.A.	Protocol Number:	Z7224L01
----------	---------------	------------------	----------

- Follow-up time (years) = Follow-up time (days) / 365.25.

Date of treatment completion will be the date of End of Treatment Visit.

Date of treatment discontinuation will be the date of End of Study Visit for subjects who discontinued the study before the End of Treatment Visit. In case a subject is lost to follow-up, the date of treatment discontinuation will be the date of last Study Visit.

Date of last Follow-up will not include any visits/calls after the end of treatment.

